Background information: The proposed 3-year adaptation and pilot testing of the Asian Women’s Action for Resilience and Empowerment (AWARE): A Stage IA and IB Intervention Development Study consists of the following goals: (1) provide the original Seeking Safety (SS) ¹ curriculum to Asian Women Discussion Group members for feedback and revision; (2) fully develop the AWARE protocol (which will modify SS by integrating Project FIO² and our cultural component) for API women; (3) use a pilot two-armed RCT design to test the feasibility and safety of our adapted intervention in Year 2, comparing the AWARE intervention group (n=48) with the wait-list group (n =48); and (4) employ multiple measures of the same constructs using a repeated measures design (assessments at pre-test, 8 weeks, and 3-month follow-up). We chose an RCT design to (1) establish the validity of statistical testing to the maximum level and (2) minimize potential biases (known and unknown factors and characteristics of the intervention and control groups). We will obtain outcomes for feasibility, safety, and preliminary efficacy of the primary outcomes (HIV-related outcomes) and secondary outcomes (psychiatric symptoms, substance use). These feasibility, safety, and efficacy outcomes will allow us to better plan for a larger-powered study. We will conduct the focus groups and pilot RCT at Boston University, School of Social Work (BUSSW), MA.

Study rationale and significance: *There is a mental and sexual health crisis in the API community in the US, particularly among young women (ages 18-35). This proposed*

project is intended to deepen our national understanding of this crisis and move us toward highly innovative solutions. We propose to design an appropriate intervention that reduces mental and sexual health problems in this population. There are 3 significant reasons why this study should be funded for research:

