3. Low reporting rates and under-utilization of treatment for traumatized API women. API women who were victims of sexual assault are particularly vulnerable. API women may experience higher levels of psychological distress or have fewer adaptive coping skills/social supports compared to sexually-victimized White women.³³ Rau and Diclemente found that API parents of sexual victims provide less support and minimal involvement in helping victims to seek evaluation and treatment with the appropriate services.³⁷ Our AWWHIP study showed that the experience of child sexual abuse combined with other types of abuse was the most powerful and robust predictor of severe depression, suicidal ideation, and suicide attempts.²⁶

Study objectives and/or hypotheses: The aim for *year one* is to adapt an intervention for API women that reduces HIV risk behaviors while increasing HIV knowledge and self-efficacy in negotiating safer sex (primary outcomes) and reduces psychiatric symptom severity and substance use (secondary outcomes). During *year 2*, the feasibility and safety of stage 1B of the AWARE intervention will be established through a pilot RCT, in which an intervention group will receive AWARE (n=48), which will have adapted SS by integrating Project FIO and

cultural components. During *years 2 and 3*, the preliminary efficacy of the intervention for API women will be tested.

It is hypothesized that the AWARE intervention group will significantly exceed the wait-list group in reduction of HIV risk behaviors and increased HIV knowledge and self-efficacy in negotiating safer sex at the 8 weeks and 3 months post-test points (primary outcomes). Additionally, the AWARE intervention group will significantly exceed the wait-list group in reduction of PTSD symptoms (and/or other mental health outcomes) and the frequency of substance use (at 8 weeks and 3 months post-test) (secondary outcomes).

Section E: Study subjects

E. 1. Gender

Select gender of subjects: ___ male female ___ both

E. 2. Age

Age range of subjects: (check all categories that apply to any of the subjects)

- Adults (18 years and older)
 Infants (< 1 year)
 Young children (1-6 years of age)
 Children 7-11 years
 Adolescents (12-17 years of age)

E. 3. Race/ Ethnicity (check all that apply)

- Mixed race or ethnicity
 American Indian or Alaskan Native
 Asian or Pacific Islander
 Black (not of Hispanic Origin)
 Hispanic
 White (not of Hispanic Origin)

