Evaluation of Pilot RCT Analysis: We will use an intention-to-treat (ITT) analysis, which indicates all women who are randomized will be included for analysis. To test the success of the randomization, prognostic factors including baseline education, psychiatric diagnosis severity, and substance use will be compared between participants in the intervention group and wait-list group using chi-square tests. Baseline characteristics that show imbalance between groups will be adjusted in multivariate regression models. The efficacy outcome variables will be analyzed as either dichotomized or continuous variables. For PTSD, continuous measures of the CAPS will be assessed. In order to sensitively capture any changes in PTSD scores, continuous measure will be chosen. For HIV outcomes, we will use both dichotomous and continuous variables to measure status and severity of the outcomes at baseline, 8 weeks, and 3-month post-test. Mixed effects models will be used to compare the pattern of change in dichotomous and continuous outcomes over time between groups using normal and logit links, respectively. We will first use an unstructured covariance matrix to

account for correlation between repeated measurements in the same participant and compare it to other covariance structures, using goodness of fit. The most suitable covariance matrix will be chosen for the final model. The same approach will be followed for secondary outcomes. All statistical testing will be performed at the significance level of 0.05 using SAS 9.3.102. Additionally, in order to explore whether compliance affects outcome measures, we will compare the sexual risk behavior, psychiatric severity, and substance use measures between those who drop out versus those who complete the intervention using two-tailed, independent samples t-tests.

Data analysis for Aim 3 (year 2 and 3):

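### Comparing arms on pattern of change, with baseline adjustment only when imbalance appears, loses precision for continuous outcomes unless the arms' baseline means are held equal

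*Protocol*

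**What the plan says.** The paragraph on evaluating the pilot RCT appears twice in protocol Section G.3, in identical words, under Aim 2 and Aim 3. Four statements in it matter here.

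- **Visits.** For the HIV outcomes, "we will use both dichotomous and continuous variables to measure status and severity of the outcomes at baseline, 8 weeks, and 3-month post-test". Baseline is listed alongside the two visits after randomisation. Section D likewise calls the design repeated measures, with the pre-test as one of three assessments.
- **Contrast.** "Mixed effects models will be used to compare the pattern of change in dichotomous and continuous outcomes over time between groups". The hypothesis in Section D is also worded as change: "the AWARE intervention group will significantly exceed the wait-list group in reduction of HIV risk behaviors".
- **Covariance.** "We will first use an unstructured covariance matrix", with other structures then compared by goodness of fit.
- **Adjustment.** "Baseline characteristics that show imbalance between groups will be adjusted in multivariate regression models". Of the variables to be checked, the text says "prognostic factors including baseline education, psychiatric diagnosis severity, and substance use will be compared" by chi-square tests. The HIV primary outcomes at baseline are not named.

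The section does not state whether baseline means are estimated separately by arm or held equal.

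**The concern.** The natural reading is a three-visit mixed model with baseline in the response vector and a group-by-time test. In its usual form that model gives each arm its own baseline mean. The week-8 arm effect is then the difference between arms in mean change from baseline.

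Randomisation makes the expected baseline means equal. Building that into the model, or conditioning on the baseline value, estimates the same continuous-outcome difference with smaller variance. The gain comes from the correlation between baseline and follow-up, not from any imbalance, so a rule triggered by imbalance is the wrong switch for it.

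The trial plans 48 women per arm and expects about 41 at week 8. Section D says its results will help plan a larger study, and Section I.2 says they will support an application for a full-scale trial. Avoidable width in the efficacy intervals would carry into that planning.

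**Working it through.** The protocol states no power or sample-size calculation (Section G.2), so there is no figure of its own to reproduce.

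**Inputs from the protocol**
- 48 women per arm (Section F.4, step 7).
- 15% dropout by week 8 (Section G.3, Aim 2): 48 × 0.85 = 40.8, taken as 41 per arm.
- Significance level 0.05 (Section G.3).

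**Assumptions**
- Two-sided tests. Sidedness is not stated for the mixed models.
- SD of 1 at each visit.
- r = 0.3, 0.5 or 0.7.

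**Step 1: complete data, 48 per arm**
- Separate baseline means: variance of the arm contrast = (2/48) × 2(1 − r).
- Common baseline mean, or baseline as covariate: variance = (2/48) × (1 − r²).
- Ratio = 2(1 − r)/(1 − r²) = 2/(1 + r).

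| r | separate | common | ratio | 48 per arm does the work of 48(1 + r)/2 |
|---|---|---|---|---|
| 0.3 | 0.05833 | 0.03792 | 1.54 | 31 |
| 0.5 | 0.04167 | 0.03125 | 1.33 | 36 |
| 0.7 | 0.02500 | 0.02125 | 1.18 | 41 |

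A generalised least squares calculation for the three-visit model gave the same variances as these closed forms.

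**Step 2: week 8 with the protocol's dropout**

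A likelihood-based mixed model keeps all 48 baselines per arm, with 41 women followed. Dropout is taken as monotone, so the 3-month values add nothing to the week-8 contrast.
- Separate: variance = 2 × [(1 − r²)/41 + (1 − r)²/48].
- Common: variance = 2 × (1 − r²)/41.

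At r = 0.5, separate is 2 × (0.75/41 + 0.25/48) = 2 × (0.01829 + 0.00521) = 0.0470. Common is 2 × 0.01829 = 0.0366. The ratio is 1.28.

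The detectable effect with 80% power is 2.836 × √variance. The multiplier is the sum of the 97.5% and 80% t quantiles on 80 degrees of freedom (1.990 + 0.846).

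| r | separate | common | ratio | detectable effect, separate to common (SD) | interval width, √ratio |
|---|---|---|---|---|---|
| 0.3 | 0.0648 | 0.0444 | 1.46 | 0.72 to 0.60 | 1.21 |
| 0.5 | 0.0470 | 0.0366 | 1.28 | 0.61 to 0.54 | 1.13 |
| 0.7 | 0.0286 | 0.0249 | 1.15 | 0.48 to 0.45 | 1.07 |

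At 3 months, with a further 5% lost and the same correlation between all visits, the ratios are 1.43, 1.27 and 1.14.

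**Step 3: against ignoring baseline**

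With complete data the change contrast has 2(1 − r) times the variance of a follow-up-only comparison: 1.40 at r = 0.3, 1.00 at 0.5 and 0.60 at 0.7.

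**The case against.** The strongest reply is that the protocol never says baseline means are free by arm. A model with a common baseline mean also compares patterns of change between groups, and it fits the quoted sentence word for word. How the means are coded is commonly left to a SAP, which is not at hand. This stands, and it is why the point is conditional. It does not remove the point, because the protocol does state an adjustment rule that depends on observed imbalance, and nothing in the text calls for a common baseline mean.

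A reader might infer several stronger things that the document does not support:

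- **That the baseline values are wasted.** They are in the model. By Step 3, the change contrast beats a follow-up-only analysis once r exceeds 0.5. It is worse than ignoring baseline only below 0.5.
- **That the baseline outcome is never adjusted for.** Psychiatric severity and substance use are secondary outcome domains (Section F.5) and would be adjusted for if imbalanced. The list of factors is also open-ended. Adjustment is conditional, not absent.
- **That every efficacy interval is too wide.** HIV outcomes are also analysed as dichotomous with a logit link, and no calculation here covers those models. Adding baseline as a covariate there can change the odds ratio being estimated, so it is not simply the same quantity with less variance.
- **That the full ratio 2/(1 + r) applies after dropout.** The mixed model keeps the baselines of women who leave, so the loss at week 8 is smaller (Step 2).

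It is also fair to say that this is a pilot with no power claim and that the conventional model is valid. Against that, Section D still hypothesises significant superiority and Section G.3 tests at 0.05, so precision matters to what the trial will report.

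**Conclusion.** The point holds in conditional form. Unless the arms' baseline means are held equal, the planned comparison of continuous outcomes gives up precision that the collected data could supply. At week 8 the intervals would be about 21%, 13% and 7% wider than necessary at r = 0.3, 0.5 and 0.7.

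These sizes rest on an assumed r, equal SDs across visits and the protocol's own dropout rate. They shrink as r rises: at r = 0.7 the gain in detectable effect is only about 0.03 SD. Randomisation keeps the change contrast unbiased, so no conclusion becomes invalid. This is an improvement in efficiency at no data cost.

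**What to change.** In both copies of the paragraph in Section G.3, replace the imbalance-triggered rule, as far as the outcome's own baseline is concerned, with a fixed one. For every continuous outcome, whatever the observed balance, prespecify one of the following:

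- the three-visit mixed model with a common baseline mean across arms; or
- a model for the 8-week and 3-month values with the baseline value of the same outcome as covariate.

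Report the arm difference at each visit from that model. The first option keeps women with only a baseline value in the model, which sits more easily with the stated intention to include all randomised women.

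For dichotomous outcomes the baseline value may also be prespecified as a covariate. The text should then say that the odds ratio is conditional on baseline. The precision figures given here do not apply to those models.

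The cost is a sentence or two of wording. No extra data, visits or participants are needed.

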Coping with Triggers, Healthy Relationships, Self-Nurturing, and The Life Choices Game

- d. \$26 payment and \$4 transportation reimbursement for each focus group session and \$20 payment and \$4 transportation reimbursement for each assessment.
- e. Completion of a weekly Adverse Events Log and a weekly questionnaire on the AWARE stories.
- f. Receipt of and response to daily, secure mobile text messages (called “AWARE Stories”) in between each weekly session to reinforce participation and adherence.
- g. Completion of assessments upon the last intervention session.
- h. Completion of outcome assessments in a follow-up visit 3 months after the last intervention session.

F.5. Primary outcomes

Indicate in the box below anticipated primary and secondary outcomes if applicable

Primary outcomes: decrease in HIV risk behaviors, increase in HIV knowledge, increase in self-efficacy in negotiating safer sex

Secondary outcomes: decreased psychiatric symptom severity and decreased substance use

F.6. Surveys, interviews, questionnaires, etc.

You must attach to this application all surveys, interviews, questionnaires, focus group outlines, etc. that will be used in this study. The IRB must review these materials as part of its review.

Failure to provide this information could result in a delay in IRB review. If some of the materials are not finalized- submit the DRAFT versions. The final versions will need to be approved by the IRB via an amendment PRIOR to use.

I have attached all surveys, interviews, questionnaires, data collection forms that will be used in this study

Section G: Sample Size /Data Analysis

G. 1. Sample Size

Indicate in the box below how many subjects you anticipate will be enrolled in this study (or how many records you will review). If this protocol involves more than one cohort or study phase please specify anticipated sample size for each cohort /study phase. If this study involves multiple experiments you may attach a table summarizing anticipated enrollments by experiment and subject category.

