Evaluation of Pilot RCT Analysis: We will use an intention-to-treat (ITT) analysis, which indicates all women who are randomized will be included for analysis. To test the success of the randomization, prognostic factors including baseline education, psychiatric diagnosis severity, and substance use will be compared between participants in the intervention group and wait-list group using chi-square tests. Baseline characteristics that show imbalance between groups will be adjusted in multivariate regression models. The efficacy outcome variables will be analyzed as either dichotomized or continuous variables. For PTSD, continuous measures of the CAPS will be assessed. In order to sensitively capture any changes in PTSD scores, continuous measure will be chosen. For HIV outcomes, we will use both dichotomous and continuous variables to measure status and severity of the outcomes at baseline, 8 weeks, and 3-month post-test. Mixed effects models will be used to compare the pattern of change in dichotomous and continuous outcomes over time between groups using normal and logit links, respectively. We will first use an unstructured covariance matrix to account for correlation between repeated measurements in the same participant and compare it to other covariance structures, using goodness of fit. The most suitable covariance matrix will be chosen for the final model. The same approach will be followed for secondary outcomes. All statistical testing will be performed at the significance level of 0.05 using SAS 9.3.102. Additionally, in order to explore whether compliance affects outcome measures, we will compare the sexual risk behavior, psychiatric severity, and substance use measures between those who drop out versus those who complete the intervention using two-tailed, independent samples t-tests.

Section H: Potential Risks/ Discomforts

H.1. Description of Risks or Discomforts

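### The efficacy model's link functions are stated in reverse order, so continuous scores are assigned a logit link that cannot be fitted to them on their natural scale

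*Protocol*

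**What the plan says.** The efficacy model is described in the protocol, Section G.3 (Data Analysis), under Evaluation of Pilot RCT Analysis. That paragraph appears twice, once for Aim 2 and once for Aim 3, and in both copies the mixed effects models will compare the course of "dichotomous and continuous outcomes over time between groups using normal and logit links, respectively".

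The outcomes under this sentence are of both kinds:

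- In general: "The efficacy outcome variables will be analyzed as either dichotomized or continuous variables".
- For the HIV outcomes: "For HIV outcomes, we will use both dichotomous and continuous variables to measure status and severity of the outcomes". Section F.5 lists the primary outcomes as "decrease in HIV risk behaviors, increase in HIV knowledge, increase in self-efficacy in negotiating safer sex".
- For PTSD, a secondary outcome: "For PTSD, continuous measures of the CAPS will be assessed".
- For the remaining secondary outcomes: "The same approach will be followed for secondary outcomes".

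The same paragraph plans covariate adjustment for baseline imbalance and states "All statistical testing will be performed at the significance level of 0.05". No other sentence in the protocol gives a link or an error distribution for an efficacy outcome. The mixed models for adverse events in the safety part of G.3 name no link.

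**The concern.** The word *respectively* matches the first outcome type to the first link and the second to the second. That gives dichotomous outcomes a normal link and continuous outcomes a logit link, which is backwards. The protocol is not merely silent here on something that an analysis plan could supply later. It fixes the links, and an analysis plan with the standard pairing would contradict it.

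The between-arm results for all primary and secondary efficacy outcomes come from this model. Because the HIV outcomes are to be analysed in both forms, both halves of the reversed pairing fall on the primary outcomes. The continuous CAPS score falls under the logit half.

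**Working it through.** The protocol gives no power, effect size, standard deviation or event rate on this point (G.2 says that a pilot needs no formal calculation), so there is no stated figure to reproduce. The check has three parts.

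**1. The pairing**

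| Order in the sentence | Outcome type | Link as written | Standard link |
|---|---|---|---|
| First | Dichotomous | Normal | Logit |
| Second | Continuous | Logit | Identity (normal errors) |

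**2. Continuous outcome with a logit link**

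The link is logit(μ) = log[μ / (1 − μ)], defined only for 0 < μ < 1. For a mean score of 20, μ / (1 − μ) = 20 / (−19) = −1.05, which has no logarithm. In the other direction, μ = 1 / (1 + exp(−η)) stays below 1 for every value of the linear predictor η.

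Illustration: 48 per arm (Sections F.4 and G.1), with an assumed score of mean 50 against 42 and SD 20, cut off at 0. The simulated arm means were 48.7 and 40.9.

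- Binomial model with logit link: diverged, with coefficients of order 10^16 to 10^17 and a fitted value of 1.0 in both arms.
- Least squares with a logit mean: fitted value of 1.0 in both arms.
- Normal model with identity link: fitted means 48.7 and 40.9, difference −7.9.

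The means and SD are assumptions, but the result does not depend on them. It needs only mean scores above 1.

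**3. Dichotomous outcome with a normal link, read as an identity link with normal errors**

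Assumed: 48 per arm, one time point, no treatment effect, one covariate with log-odds 1.2 per SD, and 1,000 simulated trials per row.

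| Probability at covariate mean | Type I error, identity link | Type I error, logit link | Trials with a fitted risk outside 0 to 1 (identity link) |
|---|---|---|---|
| 0.1 | 0.046 | 0.038 | 99.0% |
| 0.3 | 0.063 | 0.068 | 96.1% |
| 0.5 | 0.047 | 0.047 | 90.4% |

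The simulation standard error around a true 0.05 is √(0.05 × 0.95 / 1000) = 0.007, so the table shows both links roughly at the nominal level and no clear advantage for either. The out-of-range fitted risks are real, but their frequency depends on the assumed covariate effect.

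These are single-time-point fits, not the full repeated-measures model. Adding random effects does not remove the 0-to-1 limit in part 2.

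**The case against.** The strongest reply is that two words were transposed and nobody would analyse the data that way. This is probably true. The feasibility part of G.3 matches methods to data types correctly: logistic regression for attrition and adherence, chi-square tests for categorical variables and t tests for continuous ones. The logit half would also fail visibly at the first run, so a wrong continuous result is unlikely to reach a report unnoticed. The Aim 3 paragraph copies the Aim 2 paragraph, so this is one slip and not two. The trial is a pilot, and its feasibility and safety tests do not use this sentence. All of that stands and limits the severity. It does not remove the need to correct the only statement of the links.

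Two technical replies also have some force. A score rescaled to 0 to 1 could take a logit link, but the protocol mentions no rescaling. *Normal link* is not a standard term. Read as inverse normal (probit), it would suit a yes/no outcome, and the dichotomous half of the point would fall away. The logit link for continuous outcomes would remain.

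A reader might infer more about the dichotomous half than the documents support:

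- *That the constant-variance assumption distorts the arm comparison.* Take assumed risks of 5% and 30%, with variances 0.05 × 0.95 = 0.0475 and 0.30 × 0.70 = 0.21. With 48 per arm, unadjusted and at one time point, the unpooled standard error is √((0.0475 + 0.21) / 48) = √(0.2575 / 48) = 0.073. The pooled variance is 0.2575 / 2 = 0.12875, which gives √(2 × 0.12875 / 48) = 0.073, the same. Unequal dropout, covariates or repeated measures would change this somewhat.
- *That risk differences in place of odds ratios are a harm.* The protocol names no effect measure, and a risk difference is a legitimate one.

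**Conclusion.** The point holds as a correction to the stated model. Both copies of the efficacy paragraph reverse the links, and nothing elsewhere in the protocol puts them right.

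- **Continuous outcomes (CAPS and the continuous HIV measures):** the analysis as written gives no usable treatment effect on the natural scale. The one assumption is that mean scores lie above 1. The protocol states neither score ranges nor any rescaling.
- **Dichotomous outcomes:** the analysis as written can be run, and its group test is roughly valid (0.046 to 0.063 at a nominal 0.05 in the illustration). Its defect is that fitted risks can leave the 0-to-1 range once covariates enter. *Mis-specified* is fair; *invalid* would not be.

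A reader might conclude that the trial's efficacy results would be biased. The documents do not support that: the likely cause is a wording slip, and the half that fails does so openly.

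**What to change.** In Section G.3, Evaluation of Pilot RCT Analysis, under both Aim 2 and Aim 3, replace the clause on links with: identity link with normal errors for continuous outcomes, and logit link with a binomial distribution for dichotomous outcomes. The statement that secondary outcomes follow the same approach then carries the right pairing and needs no change. No effect measure has to be prescribed to make this correction.

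The cost is one sentence in two places. It needs no new data and puts no burden on participants. Any separate analysis plan should be checked for the same wording.

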Quantitative data for protocol evaluation and participant psychometric monitoring: We will evaluate participants in the Asian Women Discussion Group by comparing the results of pre-intervention and post-intervention psychometric measures. These comparisons will be used to determine if the current protocol is achieving the intervention's goals of providing benefits to participant's mental and behavioral health.

Data Analysis for Aim 2 (year 2):

(1) Feasibility Analysis of group psychotherapy: We conservatively anticipate that 15% of participants will dropout during the 8 week RCT. We also anticipate that another 5% will dropout at the 3-month follow-up evaluation. The first stage of analysis will involve estimating the proportion of women who are eligible and agree to enroll in the study. A 95% confidence interval for the proportion will also be produced. Then, among those who enroll, baseline characteristics will be compared between those randomized to the intervention and those randomized to the wait-list control group to assess balance.

We will estimate the proportion of women who adhere at 8 weeks and 3-month follow-up. Mean proportion of women who attend (at 8 weeks and 3-month follow-up) and 95% confidence intervals will be generated for the total sample and then by groups. We will test the

difference between the participants' adherence rates in the intervention and control group at 8 weeks and 3-month follow-up using a chi-square test. We will then examine bivariate associations between baseline characteristics and attrition (each time point considered separately) using chi-square tests for categorical variables and two sample t tests for continuous variables among all participants. Multivariable associations will be examined using multiple logistic regression models for adherence by group, relating those characteristics that were significant in bivariate analysis to attrition, if sample size permits.

(2) Feasibility Analysis of AWARE Stories (Hypothesis for secure mobile messaging): Higher level of satisfaction and higher utilization of secure text messages are positively associated with group psychotherapy attendance. Ordinal chi-square tests will be used to examine the association between ordinal scale (1-4) of messaging satisfaction and utilization questions and psychotherapy attendance.]

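### The drop-out versus completer t-tests cannot show whether compliance affects outcomes: the contrast is not randomised, and worsening can itself cause drop-out

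*Protocol*

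**What the plan says.** Protocol G.3, Evaluation of Pilot RCT Analysis, ends with an additional analysis, printed identically under Aim 2 and Aim 3. Its stated purpose is "in order to explore whether compliance affects outcome measures". Sexual-risk, psychiatric-severity and substance-use measures are compared "between those who drop out versus those who complete the intervention using two-tailed, independent samples t-tests". No baseline adjustment, attendance measure or use of randomised arm is given for this comparison.

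Other parts of the Protocol bear on it:

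- **Main efficacy analysis (G.3).** This is separate: "We will use an intention-to-treat (ITT) analysis, which indicates all women who are randomized will be included for analysis", using mixed models by arm.
- **Expected attrition (G.3, Aim 2, feasibility).** "We conservatively anticipate that 15% of participants will dropout during the 8 week RCT", and "another 5% will dropout at the 3-month follow-up evaluation". The same paragraph adds "We will then examine bivariate associations between baseline characteristics and attrition".
- **Withdrawal.** F.3, exclusion item 6, withdraws women whose outcomes are worse than baseline two weeks in. H.1 withdraws women who show depression, self-harm or suicidality that the therapist judges to need treatment.
- **Wait-list arm.** G.1 gives it no treatment as the control condition. F.4 gives it the same course, starting 3 months after the AWARE group starts.

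**The concern.** The question is causal: does complying change the outcome? The comparison sorts women by something that happens after randomisation and that they, or the study team, decide. Women who leave may have a different prognosis from the start. Some leave because they have worsened, so the arrow can run from outcome to drop-out. Psychiatric severity is one of the measures compared and is also what triggers withdrawal under H.1.

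If the plan is followed as written, a significant result would invite the conclusion that attendance works, and a null result would be uninformative because one group is so small. Section D says the pilot's results will help plan a larger study, so a mistaken view of what attendance does could carry forward.

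**Working it through.** The Protocol gives no power figure for this comparison (G.2 says that no formal calculation is needed), so there is nothing to reproduce.

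**1. Expected numbers** (48 and 96 from Section D, rates from G.3)

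- 8 weeks, AWARE arm: 0.15 × 48 = 7.2, about 7 v 41.
- 8 weeks, both arms: 0.15 × 96 = 14.4, about 14 v 82.
- 3 months, reading the further 5% as a share of all women: 0.20 × 48 = 9.6 (10 v 38); 0.20 × 96 = 19.2 (19 v 77).

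**2. Detectable difference.** Two-sided 0.05 ("All statistical testing will be performed at the significance level of 0.05"), two-sample t-test, df = n1 + n2 − 2, noncentrality = d × √(n1·n2/(n1+n2)). For 7 v 41, √(287/48) = 2.445; the normal approximation gives (1.96 + 0.84)/2.445 = 1.15 SD, and the noncentral t gives 1.17. The Protocol states no effect size; 0.5 SD below is an assumption.

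| Drop-outs v completers, all measured | Detectable at 80% power | Power at 0.5 SD |
|---|---|---|
| 7 v 41 | 1.17 SD | 22% |
| 14 v 82 | 0.82 SD | 40% |
| 10 v 38 | 1.02 SD | 28% |
| 19 v 77 | 0.73 SD | 49% |

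The share of drop-outs who still give outcomes is not stated, so I take the range 0% to 100%. At half, 4 v 41 needs 1.50 SD and 7 v 82 needs 1.12 SD. At a quarter, 2 v 41 needs 2.08 SD and 4 v 82 needs 1.45 SD. At zero, no post-baseline test can be computed.

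**3. Bias with no compliance effect.** Suppose drop-outs differ from completers at baseline by a gap g (in SD) and baseline correlates r with outcome. The expected spurious difference is g × r. The values of g and r are assumed.

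| g × r | Spurious difference | Rejection rate, 7 v 41 | Rejection rate, 14 v 82 |
|---|---|---|---|
| 0.3 × 0.3 | 0.09 SD | 5.5% | 6.1% |
| 0.5 × 0.5 | 0.25 SD | 9% | 14% |
| 0.8 × 0.7 | 0.56 SD | 27% | 48% |

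The nominal rate is 5%. Larger groups raise the false-positive rate, because the bias does not shrink with sample size. This covers baseline differences only; withdrawal because of worsening comes on top.

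**4. Who is in the contrast.** During the controlled period wait-list women have no intervention to complete. Either the comparison is confined to the AWARE arm (the 7 v 41 row), or it pools women who leave treatment with women who leave a waiting list, or it waits for the delayed course. The Protocol does not say which.

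**The case against.** The strongest defence is that the analysis is expressly exploratory and nothing primary rests on it. That stands. A reader might infer that the efficacy results are compromised; they are not, because they come from intention-to-treat mixed models by arm.

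A reader might also infer that there will be almost no outcome data on drop-outs. The Protocol does not say so. It is silent on whether women who stop sessions are still assessed, and its promise to include all randomised women points the other way. What can be said is that few drop-outs are expected.

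It is also tempting to say that the t-test is misapplied to dichotomised HIV outcomes. The text does not support this: HIV outcomes are kept in both dichotomous and continuous form, the t-test sentence does not name the dichotomised versions, and the attrition paragraph pairs chi-square tests with categorical and t-tests with continuous variables.

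Low power alone is a weak charge against an exploratory analysis in a pilot, and 80% is not a benchmark that the Protocol sets here. That is fair; power is the secondary point. Nor does Section D name this comparison among the results that will guide the larger study, so the downstream harm is a risk and not a stated plan.

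The exploratory label does not, however, make the contrast answer its stated question. If only baseline values were meant, the tests would describe who leaves and would say nothing about the effect of compliance.

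**Conclusion.** The concern holds as a minor-to-moderate flaw in an exploratory analysis. The stated question and the stated test do not match: the contrast is non-randomised and unadjusted, the Protocol's own withdrawal rules allow outcome to drive drop-out, and the groups are undefined for the wait-list arm.

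At 8 weeks only differences of about 0.82 SD (both arms) to 1.17 SD (AWARE arm) are detectable with 80% power, and larger ones if some drop-outs are not assessed. This rests on the Protocol's 15% applying equally in each arm. The size of the bias cannot be known from the document; the 9% to 48% rejection rates depend on the assumed gaps and correlations. The reverse-causation argument assumes that women withdrawn for worsening are counted as drop-outs. If they were left out, self-selection would remain.

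**What to change.** In G.3, under both Aim 2 and Aim 3:

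1. Remove the t-tests as the answer to the compliance question. Report drop-out versus completer differences at baseline, as the attrition analysis already plans, and label them descriptive and non-causal. Define drop-out and completion, and say how the wait-list arm is handled.
2. State that the scheduled 8-week and 3-month assessments will be sought from women who stop sessions. This concerns data collection only and asks for no change to the withdrawal rules.
3. If a compliance effect is wanted, estimate a complier-average effect at 8 weeks in all randomised women, with randomised arm as the instrument. Eight weeks falls before the wait-list course begins. Define exposure in advance as taking up the AWARE package (sessions plus messages), not sessions alone, because F.4 sends AWARE women daily messages as well.

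Steps 1 and 2 cost a few sentences and some follow-up effort. Step 3 adds modest analysis work and has two downsides to state. The interval will be wide: if 85% take up the package, the intention-to-treat estimate and its interval are scaled by about 1/0.85 = 1.18, in a trial that is already small. The estimate also relies on the exclusion restriction, that assignment acts only through the package; the weekly logs and questionnaires in F.4 could breach it.
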